HVTN 108 is one of the phase 1/2a studies planned within this program. Evaluation of DNA/protein and protein only regimens will provide an opportunity to compare the immunogenicity of these simpler, non-vector vaccine regimens. This study has 7 active arms and 1 placebo arm and will compare DNA priming administered at Months 0 and 1, followed by DNA + Protein + MF59 or AS01_B boosting at Months 3 and 6, versus DNA + Protein + MF59 or AS01_B co-administered at Months 0, 1, and 6. In addition, this study will evaluate Protein + AS01_B administered at Months 0, 1, and 6. Furthermore, to assess whether too high a protein dose in the presence of AS01_B adjuvant may overstimulate the immune system and thereby suppress responses, 2 different doses of each of the bivalent Env proteins will be evaluated: 20 mcg versus 100 mcg for each of the DNA containing regimens (see section 4.5.4).

How to identify the regimens which will be further assessed in a future efficacy trial will depend on the 'adequate take/potency' (ATP) as defined in Section 6.1.2. Meeting the ATP criteria is a necessity to move forward to efficacy testing, however in itself does not suffice for a regimen to qualify for further evaluation. Because many or all of the regimens of this study could hypothetically meet the ATP, further down-selection will be performed using secondary and exploratory objectives as described in Sections 5.2 and 5.3. In this way, those individual regimens which are able to elicit an immune response with a unique profile, and therefore warrant further evaluation, can be moved forward into a future efficacy trial. Such an efficacy trial could potentially include 1 or more of the vaccine regimens evaluated in this study, together with regimens from other phase 1/2a studies.

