4.5.6 Schedule

The vaccination schedule of the DNA prime followed by DNA+protein boost regimens is based upon the schedule used in RV144, but replaces the canarypox (ALVAC) vector immunogen with a DNA plasmid construct. The schedule for the DNA and protein co-administration and protein alone regimens is similar to the prime/boost regimens, yet administers placebo instead of active product at month 3. In previous trials with adjuvanted protein, peak immunogenicity is obtained after 3 doses of protein, while a longer rest between the 2nd and 3rd vaccinations is preferred for antibody maturation.

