Local and general solicited symptoms could be divided into 4 groups given their frequency per dose given into brackets (by decreasing order):

- Pain (between 86.3% and 96.3%) with few grade 3 symptoms (\leq 3.4%).
- Fatigue (between 33.8% and 46.6%), feverishness (between 22.9% and 53.4%), headache (between 35.0% and 48.3%) and myalgia (between 25.8% and 43.3%). Few cases of grade 3 myalgia and fatigue were reported (\leq 4.2%). For feverishness the frequency of grade 3 symptoms was 10.1% and for headache was 5.9% in the gp120/ NefTat/ AS01_B group.
- Redness, swelling, nausea and fever: the frequency of those symptoms did not exceed 30.3%. Few grade 3 nausea and fever were reported ($\leq 2.1\%$). The frequency of grade 3 redness and swelling was 20.2% and 13.9% respectively in the gp120/ NefTat/ AS01_B group.
- Diarrhea and vomiting: the frequency of these symptoms was less than or equal to 7.5%. No grade 3 diarrhea was observed, and only 0.4% of the doses were followed by grade 3 vomiting.

Almost all general symptoms (fatigue, feverishness, headache, myalgia, nausea and fever, vomiting) were considered as related to the vaccination, except for diarrhea.

The duration of general symptoms was less than or equal to 2 days in most cases whereas the duration of local symptoms was often more than 2 days. In the gp120/ NefTat/AS01B group the overall frequency of the general symptoms tended to be higher after the 2nd, 3rd, or 4th dose of vaccine compared to the first dose (but not for all symptoms and all groups).

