Reactogenicity was higher during the 7-day period after each vaccine dose in the F4/AS01 groups than in the F4 in WFI groups. The incidence of local and general symptoms tended to be higher in the F4/AS01 groups after the second vaccine dose. Pain was the most common solicited local symptom, reported after 96.0%–98.0% of doses in the F4/AS01 groups and after 10.0%–30.0% of doses in the F4 in WFI groups (grade 3 severity after 5.0%-10.1% of doses in the F4/AS01 groups). Fatigue was the most common solicited general symptom, reported after 66.0%-77.8% and 30.0%-45.0% of doses in the F4/AS01 and F4 in WFI groups, respectively (grade 3 severity after 7.0%-12.1% of doses in the F4/AS01 groups). Fever of more than 39°C was reported in 3.0%, 2.0% and 1.0% of the doses in the respective 10, 30 and 100 mcg F4/AS01 groups). No solicited local or general grade 3 symptoms were reported in the F4 in WFI groups. No differences in reactogenicity were observed between the antigen dose levels in the F4/AS01 groups. During the 30-day postvaccination period, 60.0%-84.0% of subjects in the F4/AS01 groups reported unsolicited symptoms, compared with 50.0%–70.0% in the F4 in WFI groups. In the F4/AS01 groups, unsolicited symptoms (mainly chills and injection site reactions) were considered causally related to vaccination in 30.0%-44.0% of subjects and were of grade 3 severity in <10.0%. All related symptoms were transient and resolved without sequelae, generally within 2–3 days. Six serious adverse events were reported in the F4/AS01 groups, all considered unrelated to vaccination No subjects died during the study period, and no subject withdrew because of adverse events.

ECR 004, a subset of volunteers primed 3 years before with 2 doses F4 10 mcg / AS01B (PRO HIV-005) received a (third) single booster dose of F4 10 mcg / AS01B.

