5.1 Primary objectives and endpoints

Primary objective 1

• To evaluate the safety and tolerability of DNA and/or different doses of clade C bivalent gp120 protein with either MF59 or AS01_B adjuvant in various regimens in HIV uninfected healthy adults.

Primary endpoints 1

- Severe local and systemic reactogenicity signs and symptoms (pain, tenderness, erythema, induration, fever, malaise/fatigue, myalgia, headache, nausea, vomiting, chills, arthralgia) up to 7 days after each vaccine dose
- AEs by body system, Medical Dictionary for Regulatory Activities (MedDRA) preferred term, severity, and assessed relationship to study products up to 30 days after each vaccine dose
- SAEs, AESIs, and new chronic conditions (requiring medical intervention for \geq 30 days) throughout the study
- Laboratory measures: white blood cells (WBC), neutrophils, lymphocytes, hemoglobin, platelets, alanine aminotransferase (ALT), aspartate aminotransferase (AST), alkaline phosphate (ALP), and creatinine at baseline and following vaccinations
- AEs leading to early participant withdrawal or early discontinuation of study products administration throughout the study.

Primary objective 2

• To evaluate the systemic immune responses at the Month 6.5 timepoint (2 weeks after the 4th vaccination) of clade C DNA, bivalent gp120 protein/MF59, and/or bivalent gp120 protein/AS01_B in each vaccine regimen

Primary endpoints 2

- HIV-specific total IgG binding antibody response breadth and magnitude as assessed by multiplex assay.
- Anti –V1/V2 scaffold IgG binding antibody responses as assessed by multiplex assay.
- Neutralizing antibody responses against HIV-1 isolates.
- HIV-specific CD4+ and CD8+ T-cell responses as assessed by flow cytometry.

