6.4.3.1 Reactogenicity

The number and percentage of participants experiencing each type of reactogenicity sign or symptom will be tabulated by severity and treatment group and the percentages displayed graphically by group. For a given sign or symptom, each participant's reactogenicity will be counted once under the maximum severity for all injection visits. In addition, to the individual types of events, the maximum severity of local pain or tenderness, induration or erythema, and of systemic symptoms will be calculated. Kruskal-Wallis tests will be used to test for differences in severity between groups.

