6.4.3.3 Local laboratory values

Box plots of local laboratory values will be generated for baseline values and for values measured during the course of the study by treatment group and visit. Each box plot will show the first quartile, the median, and the third quartile. Outliers (values outside the box plot) will also be plotted. If appropriate, horizontal lines representing boundaries for abnormal values will be plotted.

For each local laboratory measure, summary statistics will be presented by treatment group and timepoint, as well as changes from baseline for postenrollment values. In addition, the numbers (percentages) of participants with local laboratory values recorded

as meeting Grade 1 AE criteria or above as specified in the DAIDS AE Grading Table (see Section 11.2) will be tabulated by treatment group for each postvaccination timepoint. Reportable clinical laboratory abnormalities without an associated clinical diagnosis will also be included in the tabulation of AEs described above.

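### Section 6.4.3.1 summarises reactogenicity only as one maximum per participant over all vaccination visits; a by-visit table is needed to show severe rates by dose and for DNA without protein

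*Combined protocol and SAP*

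**What the plan says.** The first safety endpoint in Section 5.1 is severe local and systemic reactogenicity "up to 7 days after each vaccine dose". The objective it serves begins "To evaluate the safety and tolerability of DNA and/or different doses of clade C bivalent gp120 protein" and goes on to name the two adjuvants and the various regimens.

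Section 6.4.3.1 gives counts and percentages by severity and treatment group, with this counting rule: "For a given sign or symptom, each participant's reactogenicity will be counted once under the maximum severity for all injection visits". The composite maxima and the planned rank test are not split by visit either. Laboratory values are handled differently in Section 6.4.3.3: the numbers meeting AE grades "will be tabulated by treatment group for each postvaccination timepoint".

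The four vaccination visits do not deliver the same thing (Table 3-1). Section 4.3 says that the study "will compare DNA priming administered at Months 0 and 1", followed by DNA plus adjuvanted protein at Months 3 and 6 (groups 1-3), with co-administration from Month 0. Section 4.5.6 says that the co-administration and protein-alone schedule follows the prime/boost one, "yet administers placebo instead of active product at month 3" (groups 4-7). Under Section 9.11, reactions are assessed for seven full days after every vaccination, so data by visit will exist.

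**The concern.** If every visit gave the same product, a maximum over visits would lose little. Here it merges unlike visits within each row. In groups 1-3 two priming visits without protein are merged with two visits that include adjuvanted protein. In groups 4-7 three protein visits are merged with one saline visit. No arm receives DNA alone throughout, so the priming visits of groups 1-3 are this trial's only observations on DNA without protein.

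Three quantities cannot be read from the planned table: the severe rate after a given dose, the severe rate for DNA without protein, and any change with dose number. The last has some background in the documents. Section 4.8.3 reports for an earlier AS01B vaccine that the overall frequency of "general symptoms tended to be higher after the 2nd, 3rd, or 4th dose of vaccine compared to the first dose", and adds that this did not hold for all symptoms and groups. The sponsor would need these quantities to say which component or which dose drives severe reactions in a regimen that may go forward.

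**Working it through.** **The plan's own figures.** Section 6.1.1 uses the score method. For zero events the 95% upper limit is z²/(n + z²), with z² = 3.84.
- n = 50: 3.84/53.84 = 7.1%, as stated.
- 90% chance of at least one event: 1 − 0.1^(1/50) = 4.5%, as stated.

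**Group sizes (Table 3-1, HVTN 108 alone).** Groups 1-3: 30 + 50 + 50 = 130. Groups 4-7: 30 + 50 + 50 + 50 = 180. Group 8: 24.

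Except in step 4, the per-visit severe rates below are assumptions chosen for illustration. None comes from the documents.

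**1. Dose number.** Under independence, the proportion ever severe is 1 − Π(1 − p).
- Rising 2%, 6%, 14%: 1 − 0.98 × 0.94 × 0.86 = 20.8%.
- Flat 7.5% (7.47% unrounded): 1 − (0.9253)³ = 20.8%.

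Either pattern appears as about 10/50 (score 95% CI 11.2-33.0%). Independence is not essential. With a latent within-person correlation of 0.3 the rising pattern gives about 19%, matched by a flat 7.7%; with 0.6 it gives about 17%, matched by a flat 8.2%. A by-visit table would show 1/50 (0.4-10.5%), 3/50 (2.1-16.2%) and 7/50 (7.0-26.2%). Over groups 5-7 (n = 150), dose 1 against dose 3 would be 3/150 (0.7-5.7%) against 21/150 (9.3-20.5%).

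**2. DNA without protein.** Let d be the severe rate at each priming visit and b the rate at each DNA-plus-protein visit. Ever severe in groups 1-3 is 1 − (1 − d)²(1 − b)².
- d = 0, b = 10.6%: 20.1%.
- d = 8%, b = 2.8%: 20.0%.
- d = 10.6%, b = 0: 20.1%.

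These three are indistinguishable in the planned table. With b fixed at 10%, moving d through 0, 1% and 3% changes the result only from 19.0% to 20.6% to 23.8%. At correlation 0.6 the whole movement is from about 16% to about 18%.

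**3. What a by-visit row gives.** With 130 vaccinated, zero severe events bound the rate at 3.84/133.84 = 2.9%, and there is a 90% chance of at least one event at a true rate of 1 − 0.1^(1/130) = 1.8%. For saline, 0/24 in group 8 gives an upper limit of 13.8%; 0/180 at Month 3 in groups 4-7 gives 2.1% if nobody misses that visit.

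**4. The documents' own per-dose figure.** For fatigue in the earlier F4/AS01 study, Section 4.8.3 gives "grade 3 severity after 7.0%-12.1% of doses in the F4/AS01 groups". Carried to three doses, 7.0% per dose means 7.0% of participants ever severe under complete dependence and 1 − 0.93³ = 19.6% under independence. For 12.1% the range is 12.1% to 1 − 0.879³ = 32.1%. That study used a different antigen and two doses, so this shows only how loosely per-dose and per-participant rates are linked.

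**The case against.** The strongest reply is that the endpoint wording sets a collection window and not a unit of analysis. The version history describes the change to that text as one to the assessment period. The AE endpoint is worded in parallel, over 30 days, and Section 6.4.3.2 also counts each participant once at maximum severity. The objective refers to regimens, Section 4.5 evaluates each combination as its own regimen, and Section 6.1.1 treats safety precision by regimen. All of this stands: the maximum is a legitimate regimen summary, and the issue is lost information, not a contradiction.

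Three stronger readings are tempting, and the documents do not support them.
- A reader might infer that per-dose severe rates will never be reported. The protocol refers to a separate SAP that is not in the supplied text, and the visit-level data will exist.
- A reader might infer that the table mixes two-protein-visit and three-protein-visit regimens. It does not: rows are treatment groups, and each group has a fixed schedule.
- A reader might infer that the documents report severe reactions rising with AS01B dose number. Section 4.8.3 describes overall symptom frequency or incidence, with the exceptions noted above.

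It is also fair that other trials of this DNA product (Section 4.8.1) supply safety data, and that no planned analysis asks for a DNA-only rate or a comparison with the earlier per-dose figures. The SAE listing gives the number of vaccinations received, but a severe reaction that is not an SAE would not appear there. SMB reviews are described as cumulative.

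**Conclusion.** The point holds as a modest, inexpensive improvement. As written, Section 6.4.3.1 yields no severe rate after each dose, none for DNA without protein, and no view of change by dose number, although visits differ in content by design and laboratory values already get a by-timepoint table. The loss can be material: under the assumed rates, clearly different dose patterns give the same 20.8%, and three very different DNA and protein contributions all give about 20%. The firmest gain is the 130 participants at the priming visits, where zero events would bound the severe rate at 2.9%, assuming all 130 are vaccinated at the visit concerned.

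The conclusion rests on the supplied text containing no by-visit table. The size of the loss depends on assumed rates and within-person correlation; that the maximum cannot separate the visits does not.

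**What to change.** Keep the maximum as the regimen summary. Add to Section 6.4.3.1 one descriptive table by vaccination visit and group, with participants vaccinated at that visit as denominator. It should give the number and percentage with any severe or worse local reaction, and with any severe or worse systemic reaction, with score 95% intervals as in Table 6-2. Add summary rows by what was injected: DNA without protein (groups 1-3, Months 0 and 1), each protein/adjuvant dose in order, and saline only (groups 4-7 at Month 3, and group 8, shown separately). Add no tests. Include HVTN 111 in groups 1 and 4 where its reactogenicity was collected in the same way; the supplied text does not describe that collection.

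The cost is one table and a few sentences, with no new data from HVTN 108. The downsides are about four times as many cells and wide intervals in single groups of 30 to 50. Month 3 saline in groups 4-7 follows earlier active vaccination, so it may not be comparable with group 8. If the separate SAP already has such a table, align the protocol wording with it.

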8.1 Vaccine regimen

The schedule of vaccination is shown in Section 3 and additional information is given below.

Group 1

Treatment 1 (T1): DNA-HIV-PT123 (4 mg/mL) 4 mg to be administered as 1 mL IM in the LEFT deltoid (unless medically contraindicated) at Months 0 and 1

AND

Placebo for Bivalent Subtype C gp120 / MF59 (Sodium Chloride for Injection, 0.9%) to be administered as 0.5 mL IM in the RIGHT deltoid (unless medically contraindicated) at Months 0 and 1

AND

Placebo for Bivalent Subtype C gp120 / $AS01_B$ (Sodium Chloride for Injection, 0.9%) to be administered as 0.75 mL IM in the RIGHT deltoid (unless medically contraindicated) at Months 0 and 1;

THEN

DNA-HIV-PT123 (4 mg/mL) 4 mg to be administered as 1 mL IM in the LEFT deltoid (unless medically contraindicated) at Months 3 and 6

AND

Bivalent Subtype C gp120 / MF59 (an admixture of 100 mcg of TV1.C gp120, 100 mcg of 1086.C gp120, and MF59C.1) to be administered as 0.5 mL IM in the RIGHT deltoid (unless medically contraindicated) at Months 3 and 6

AND

Placebo for Bivalent Subtype C gp120 / $AS01_B$ (Sodium Chloride for Injection, 0.9%) to be administered as 0.75 mL IM in the RIGHT deltoid (unless medically contraindicated) at Months 3 and 6.

Group 2

Treatment 2 (T2): DNA-HIV-PT123 (4 mg/mL) 4 mg to be administered as 1 mL IM in the LEFT deltoid (unless medically contraindicated) at Months 0 and 1

AND

Placebo for Bivalent Subtype C gp120 / MF59 (Sodium Chloride for Injection, 0.9%) to be administered as 0.5 mL IM in the RIGHT deltoid (unless medically contraindicated) at Months 0 and 1

AND

Placebo for Bivalent Subtype C gp120 / $AS01_B$ (Sodium Chloride for Injection, 0.9%) to be administered as 0.75 mL IM in the RIGHT deltoid (unless medically contraindicated) at Months 0 and 1;

THEN

DNA-HIV-PT123 (4 mg/mL) 4 mg to be administered as 1 mL IM in the LEFT deltoid (unless medically contraindicated) at Months 3 and 6

AND

Placebo for Bivalent Subtype C gp120 / MF59 (Sodium Chloride for Injection, 0.9%) to be administered as 0.5 mL IM in the RIGHT deltoid (unless medically contraindicated) at Months 3 and 6

AND

Bivalent Subtype C gp120 / $AS01_B$ (an admixture of 100 mcg of TV1.C gp120, 100 mcg of 1086.C gp120, and $AS01_B$) to be administered as 0.75 mL IM in the RIGHT deltoid (unless medically contraindicated) at Months 3 and 6.

Group 3

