Treatment 3 (T3): DNA-HIV-PT123 (4 mg/mL) 4 mg to be administered as 1 mL IM in the LEFT deltoid (unless medically contraindicated) at Months 0 and 1

AND

Placebo for Bivalent Subtype C gp120 / MF59 (Sodium Chloride for Injection, 0.9%) to be administered as 0.5 mL IM in the RIGHT deltoid (unless medically contraindicated) at Months 0 and 1

AND

Placebo for Bivalent Subtype C gp120 / $AS01_B$ (Sodium Chloride for Injection, 0.9%) to be administered as 0.75 mL IM in the RIGHT deltoid (unless medically contraindicated) at Months 0 and 1;

THEN

DNA-HIV-PT123 (4 mg/mL) 4 mg to be administered as 1 mL IM in the LEFT deltoid (unless medically contraindicated) at Months 3 and 6

AND

Placebo for Bivalent Subtype C gp120 / MF59 (Sodium Chloride for Injection, 0.9%) to be administered as 0.5 mL IM in the RIGHT deltoid (unless medically contraindicated) at Months 3 and 6

AND

Bivalent Subtype C gp120 / $AS01_B$ (an admixture of 20 mcg of TV1.C gp120, 20 mcg of 1086.C gp120, and $AS01_B$) to be administered as 0.75 mL IM in the RIGHT deltoid (unless medically contraindicated) at Months 3 and 6.

Group 4

Treatment 4 (T4): DNA-HIV-PT123 (4 mg/mL) 4 mg to be administered as 1 mL IM in the LEFT deltoid (unless medically contraindicated) at Months 0, 1 and 6

AND

Bivalent Subtype C gp120 / MF59 (an admixture of 100 mcg of TV1.C gp120, 100 mcg of 1086.C gp120, and MF59C.1) to be administered as 0.5 mL IM in the RIGHT deltoid (unless medically contraindicated) at Months 0, 1 and 6

AND

Placebo for Bivalent Subtype C gp120 / $AS01_B$ (Sodium Chloride for Injection, 0.9%) to be administered as 0.75 mL IM in the RIGHT deltoid (unless medically contraindicated) at Months 0, 1 and 6;

AND

Placebo for DNA (Sodium Chloride for Injection, 0.9%) to be administered as 1 mL IM in the LEFT deltoid (unless medically contraindicated) at Month 3

AND

Placebo for Bivalent Subtype C gp120 / MF59 (Sodium Chloride for Injection, 0.9%) to be administered as 0.5 mL IM in the RIGHT deltoid (unless medically contraindicated) at Month 3

AND

Placebo for Bivalent Subtype C gp120 / $AS01_B$ (Sodium Chloride for Injection, 0.9%) to be administered as 0.75 mL IM in the RIGHT deltoid (unless medically contraindicated) at Month 3.

Group 5

Treatment 5 (T5): DNA-HIV-PT123 (4 mg/mL) 4 mg to be administered as 1 mL IM in the LEFT deltoid (unless medically contraindicated) at Months 0, 1 and 6

AND

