8.3.1 DNA-HIV-PT123

One vial of DNA-HIV-PT123 (labeled as DNA-HIV-PT123 [4 mg/mL]) will be needed to prepare the dose. Prior to dispensing, the pharmacist will remove the study product from the freezer and allow it to thaw at room temperature.

Once thawed, the pharmacist, using aseptic technique, will gently swirl the vial and then withdraw 1 mL into a syringe. The syringe should be no smaller than 1.5 mL syringe and no larger than a 5 mL syringe.

The syringe should be labeled as "DNA 4 mg or Placebo 1 mL" and have an overlay to maintain blinding. The syringe must also be labeled for administration in the LEFT deltoid. The study product should be administered as soon as possible after preparation.

Any partial vials or expired filled syringes should be autoclaved immediately prior to disposal and disposed of in accordance with institutional or pharmacy policy.

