The syringe should be labeled as "Bivalent Subtype C gp120 / MF59 or Placebo 0.5 mL" and have an overlay to maintain blinding. The syringe must also be labeled for administration in RIGHT deltoid. The syringe containing study product should be bagged for transport to the clinic where it will be administered. This study product should be administered immediately, defined as within 30 minutes as per IAC recommendations. If this is not possible, the site pharmacist may be permitted to label the syringe with a DO NOT USE AFTER 2 hour date and time from preparation. In this case, the vaccine should be stored at 2°C - 8°C until administration and if not used within 2 hours, it should be discarded.

Any unused portion of reconstituted vials or expired prefilled syringes is disposed of in accordance with institutional or pharmacy policy for a biological safety level S1 product.

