9.11.1 Assessment of systemic and local symptoms

Systemic symptoms include increased body temperature, malaise and/or fatigue, myalgia, headache, chills, arthralgia, nausea, and vomiting. Local symptoms include pain and/or

tenderness proximal to the injection site. The daily maximum severity reached for each symptom during the assessment period is reported.

Body temperature is measured by oral or infrared thermometry and reported in degrees Celsius. If temperature is measured in Fahrenheit, the conversion to Celsius should be documented in the participant's chart note. A measurement is taken once daily during the assessment period and should be repeated if participant is feeling feverish.

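### Local reactogenicity is summarised as one participant-level maximum, with no split by deltoid or visit, so the planned tables cannot separate DNA's local reactions from those of the adjuvanted protein

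*Combined protocol and SAP*

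**What the plan says.** Products are assigned to sides. In Section 8.1, Groups 1-3 receive DNA "4 mg to be administered as 1 mL IM in the LEFT deltoid (unless medically contraindicated) at Months 3 and 6", as they also do at Months 0 and 1. At Months 3 and 6 the protein/AS01B of Groups 2 and 3 is "to be administered as 0.75 mL IM in the RIGHT deltoid (unless medically contraindicated) at Months 3 and 6"; Group 1 receives protein/MF59 on the same side. Groups 4-6 receive DNA "4 mg to be administered as 1 mL IM in the LEFT deltoid (unless medically contraindicated) at Months 0, 1 and 6", each time with adjuvanted protein on the right. Group 7 has saline on the left throughout and Group 8 has saline on both sides. The pharmacy instructions agree. For DNA (8.3.1): "The syringe must also be labeled for administration in the LEFT deltoid". For protein/MF59 (8.3.3): "The syringe must also be labeled for administration in RIGHT deltoid".

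The analysis does not carry the side forward. For pain and tenderness, Section 9.11.1 says: "The daily maximum severity reached for each symptom during the assessment period is reported". It does not mention the arm. Section 6.4.3.1 takes each participant's worst grade per sign over all injection visits, adds composites ("the maximum severity of local pain or tenderness, induration or erythema, and of systemic symptoms will be calculated") and compares groups by Kruskal-Wallis. By contrast, Section 6.4.3.3 tabulates laboratory values by group and timepoint.

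Primary objective 1 (Section 5.1) covers the tolerability of DNA as well as of the protein doses and adjuvants. Its reactogenicity endpoint is severe signs and symptoms.

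**The concern.** Because the products go in different arms, left-arm reactions can be compared between groups as DNA v saline, and right-arm reactions as one adjuvant or protein dose v another. A single maximum over both arms and all visits discards this.

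Two separate losses follow. First, the maximum over visits absorbs the DNA-plus-saline visits of Groups 1-3 into their later protein visits. Second, at co-administration visits the maximum over arms lets a right-arm adjuvant reaction hide a left-arm DNA reaction of equal or lower grade. A by-visit table repairs the first loss but not the second: in Groups 4-6 every DNA dose is given alongside adjuvanted protein. In the other direction, left-arm reactions dilute the right-arm MF59 v AS01B and 20 v 100 mcg contrasts.

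At stake is the local part of the statement on DNA's tolerability. A null result on the both-arm maximum could be read as DNA adding nothing locally, when the comparison had little chance of showing otherwise.

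**Working it through.** **Plan's own figure.** The plan gives no operating characteristic for by-product reactogenicity. The nearest is Section 6.1.1: a 90% chance of at least one event in 50 at a true rate of 4.5%. This reproduces: 1 - 0.955^50 = 0.900. It is not in dispute.

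**How much DNA is co-administered** (Table 3-1). Groups 1-3 and Groups 4-6 each have 30 + 50 + 50 = 130 participants.
- DNA doses: 130 x 4 + 130 x 3 = 910.
- With adjuvanted protein: 130 x 2 + 130 x 3 = 650, or 71%.
- With saline only on the right: 130 x 2 = 260 (Groups 1-3, Months 0 and 1).

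**Right-arm background.** Section 4.8.3, for an earlier gp120/NefTat trial with three adjuvants, one of them AS01B, gives per dose: "Pain (between 86.3% and 96.3%) with few grade 3 symptoms", the latter at most 3.4%.

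**Any-grade pain, Group 6 v Group 7, 50 each, one visit.** These groups share the 20 mcg dose, AS01B and schedule, and differ only in DNA. Assume left-arm pain of 40% with DNA and 10% with saline, and independent arms. With right-arm rate r, the both-arm rate is 1 - (1 - r)(1 - left rate).
- r = 0.863: 1 - 0.137 x 0.60 = 91.8% v 1 - 0.137 x 0.90 = 87.7%.
- r = 0.963: 1 - 0.037 x 0.60 = 97.8% v 1 - 0.037 x 0.90 = 96.7%.

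Power by full enumeration, two-sided Fisher at 5%:

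| Left-arm pain, DNA v saline (assumed) | Left arm only | Both arms, r = 0.863 | Both arms, r = 0.963 |
|---|---|---|---|
| 40% v 10% | 92.7% | 4.6% | 0.2% |
| 40% v 20% | 51.5% | 2.9% | 0.1% |
| 50% v 30% | 46.3% | 2.8% | 0.1% |

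**Same contrast with the planned test.** Kruskal-Wallis on the maximum over three active visits, 4,000 simulated trials. Assumed left-arm grades 0/1/2/3 are 50/40/9/1% (DNA) and 80/18/2/0% (saline). The right arm has no pain in 3.7% or 13.7% of doses and grade 3 in 3.4%; the split between grades 1 and 2 is assumed. Power is about 8-11% on the both-arm maximum and above 99% on the left-arm maximum.

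**DNA-plus-saline visits, Groups 1-3 (130) v Group 8 (24).** Keep 40% v 10% on the left and assume 10% saline pain on the right in both groups. Even with arms combined, the rates are 1 - 0.60 x 0.90 = 46% v 1 - 0.90 x 0.90 = 19%, and Fisher power at one visit is 71%. The maximum over all visits removes this view. If doses are independent, right-arm pain at one or more of two protein visits has probability 1 - 0.137^2 = 98.1% to 1 - 0.037^2 = 99.9%.

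**Severe pain, Group 6 v Group 7.** Assume 15% v 0% on the left and 3.4% on the right.
- Left arm only: power 78%.
- Both arms, one dose: 1 - 0.966 x 0.85 = 17.9% v 3.4%, power 53%.
- Both arms, right-arm risk accumulated over three doses (1 - 0.966^3 = 9.9%) with the left-arm rate held at 15%: 23.4% v 9.9%, power 34%.

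**The case against.** The strongest reply is that the regimen is the intended unit. Objective 1 speaks of regimens, and Section 4.5 evaluates each combination as its own regimen. A participant-level maximum answers that question, and this stands: the existing summary is not an error.

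It is also fair that the primary reactogenicity endpoint is severe reactions, where pain is not at ceiling. In the same earlier trial, redness and swelling of any grade did not exceed 30.3%. The large power loss therefore belongs to any-grade pain. Even so, grade 3 redness of 20.2% and swelling of 13.9% in that trial's AS01B group are a right-arm background that would dilute a left-arm signal, and Section 6.4.3.1 analyses all grades.

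Four stronger readings are tempting but unsupported.
- A reader might infer that Group 6 v Group 7 is the sole comparison isolating DNA. Groups 1-3 v Group 8 at Months 0 and 1 also does so, without adjuvant.
- A reader might infer that the pooled analysis must show no DNA effect. It has little ability to detect one for any-grade pain and keeps moderate ability for severe pain.
- A reader might treat the two arms as a within-participant control. At co-administration visits neither arm is saline-only, and the right arm always takes two injections to the left arm's one. The DNA comparison is between groups.
- A reader might infer that side goes unrecorded. Sections 9.11.1 and 9.11.2 are silent on this. The symptom log, the CRFs and the separate SAP to which the protocol defers some analysis detail are not in the file.

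**Conclusion.** The point holds as a gap in the planned tables, and closing it is an inexpensive improvement. As written, Section 6.4.3.1 cannot separate DNA's local reactions from the adjuvanted protein's at the 71% of DNA doses that are co-administered, and it merges the remaining 29% with later protein visits.

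For any-grade pain in Group 6 v Group 7, Fisher power falls from 93% to 5% or less under the 40% v 10% assumption; the planned Kruskal-Wallis test shows the same pattern. For severe pain the fall is from 78% to 53% at one dose, under the assumed rates.

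These sizes rest on assumed left-arm rates, on independence between arms, and on a pain range spanning three adjuvants rather than AS01B alone. No ceiling is shown for MF59, although the missing split applies to those groups too. That the tables lack a split by deltoid and visit does not depend on any of these assumptions.

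**What to change.** In Section 6.4.3.1, keep the participant-level maximum as the regimen summary and add tables of local signs and symptoms by deltoid and by vaccination visit:
- left arm, DNA v saline between groups: Group 6 v Group 7 at Months 0, 1 and 6, and Groups 1-3 v Group 8 at Months 0 and 1;
- right arm, for the adjuvant and protein-dose contrasts.

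In Section 9.11.1, state that local pain and tenderness are recorded separately for each deltoid. Add a left/right field if the symptom log and CRF lack one. For injections given at an alternate site under Section 8.4, state that any reaction is tabulated with the deltoid it replaces.

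The cost is at most one extra field, slightly more for participants to enter, and a second set of descriptive tables. Doses, schedule, blinding, sample size and visits do not change. If side is not already captured, the field should be added promptly, because it cannot be reliably reconstructed later.
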